1.5 OVERALL SYNOPSIS OF THE CLINICAL INVESTIGATION

ANSM registration #:	2023-A01479-36
Clinical investigation plan #:	23E1077
Title of the clinical investigation:	SAFETY AND EFFECTIVENESS CLINICAL EVALUATION OF THE RANGE OF INJECTABLE MEDICAL DEVICES VISCOL IN AESTHETIC TREATMENT
Sponsor:	KYLANE LABORATOIRES SA [name] SWITZERLAND
Development phase	Exploratory study
Objectives:	
The primary objective is to evaluate the effectiveness of the VISCOL range used on different treated zones (facial and body areas) one month (M1) after treatment using clinical evaluation of the global aesthetic improvement (GAIS) rated by an independent investigator.
 
The secondary objectives of the study are to collect data for the VISCOL range on:
 
- the effectiveness of the range used on different treated zones four months (M4) after treatment using clinical evaluation of the global aesthetic improvement (GAIS) rated by an independent investigator.- the effectiveness on the improvement of facial skin quality by objective measurements of skin biomechanical parameters using Cutometer® and skin hydration using Moisturemeter® one (M1) and four (M4) months after treatment.- subject's satisfaction and subject's opinion on aesthetic improvement on the different treated zones using clinical evaluation of the GAIS at M1 and M4.- the injector's satisfaction on the injection quality using subjective evaluation questionnaire after injection on D0.- the safety using clinical evaluation of the Injection Site Reactions (ISR) rated by the subject and the investigator, and by collection of adverse events (AEs) at Day 0 (D0) one month (M1), four months (M4) and six months (M6). 
Another objective will be to illustrate the device effectiveness by realization of face and body macrophotographs.

Design:	◆ Open study, ◆ intra-individual, ◆ single dose, ◆ single centre.
Planned Sample Size:	86 subjects in total divided in 2 groups, according to the kind of treated zone: Group 1 (VISCOL Face): 64 subjects treated by VISCOL (one injection on D0) on both sides of the face in the following areas: malar and sub-malar areas (obligatory areas) and optional areas mandibular and/or chin. Group 2 (VISCOL Body): 22 subjects treated by VISCOL (one injection on D0) on both sides in the following areas: decolletage and neck areas (obligatory areas) and one optional area abdomen or internal face of the arm.

Number of investigational study sites:	1 (Eurofins Dermascan Pharmascan in France)
Inclusion criteria:	
1. Healthy Subject.2. Sex: male or female.3. Age: between 35 and 70 years.4. Subject seeking an improvement of her/his face (at least malar and sub-malar areas and optionally mandibular and/or chin areas) or body (at least decolletage/neck areas and optionally abdomen or internal face of the arm areas) aspect with HA skin quality improvement product.5. For Group 1 (Face): Subjects with dry skin (skin hydration rate on cheekbones < 60UA confirmed using Corneometer® measurement).6. For Group 2 (Body): If applicable: subject with mild to moderate laxity of the tissues of the internal face of the arms (from 1 to 3 on Bazin Texture of the arm scale) or the abdomen (from 2 to 5 on Bazin Abdomen texture scale)7. For Group 2 (Body): Subject with BMI <30.8. Subject whose weight did not fluctuate in the last 6 months and who agrees to keep a stable weight during the study.9. Subject having given his/her free, express, and informed consent.10. Subject psychologically able to understand the information related to the study, and to give their written informed consent.11. Subject registered with a social security scheme.12. Women of childbearing potential should use a contraceptive method considered effective since at least 12 weeks and throughout the study.
Exclusion criteria:	
In terms of population
 
1. Pregnant or nursing woman or planning a pregnancy during the study.2. Subject who had been deprived of their freedom by administrative or legal decision or who is under guardianship.3. Subject in a social or sanitary establishment.4. Subject suspected to be non-compliant according to the investigator's judgment.5. Subject having received a total of 6.000 euros as compensations for their participation in clinical research in the last 12 months, including their participation in the present study.6. Subject enrolled in another study or whose non-enrollment period is not over.7. Subject with scar(s), mole(s), hair or any other lesion on the studied zones which might interfere with the evaluation (tattoo, permanent make-up...). 
In terms of associated pathology
 
8. Subject suffering from a severe or progressive disease or any other pathology that may interfere with the evaluation of the study results and/or subject safety.9. Subject with known history of or suffering from autoimmune disease and/or immune deficiency.10. Subject suffering from active disease such as inflammation, infection, tumours, inflammatory and/or infectious cutaneous disorders (herpes, acne, rosacea, porphyria ...) in the 6 months before screening visit.11. Subject with a history of streptococcal disease or an active streptococcus infection.12. Subject prone to develop inflammatory skin conditions or having tendency to bleeding disorders.

13. Subject predisposed to keloids or hypertrophic scarring or having healing disorders.
14. Subject having history of severe allergy or anaphylactic shock including known risk of hypersensitivity to one of the components of the composition of the investigational device, to antiseptic solution (Diaseptyl®) or to amide-type anaesthetics (EMLA®), related to previous or current treatments.
15. Subject with symptoms consistent with COVID-19 or are suffering from previous COVID-19 infection.
16. Subject with previous hypersensitivity reactions to hyaluronic acid injections after a COVID-19 vaccination.

Related to previous or ongoing treatment

17. Subject having received a dose of COVID-19 vaccine within the 3 weeks prior to injection visit or planning to receive a dose in the 2 weeks following injection.
18. Any medication which may interfere, at the interpretation of the investigator, with the study objectives.
19. Subject having received treatment with a laser, ultrasound or radiofrequency treatment, a dermabrasion, a surgery, a chemical peeling or any other procedure based on active dermal response on the treated areas within the past 6 months or who plans to undergo any of these procedures during the study.
20. Subject having received within the past 18 months or planning to receive during the study any injections outside of those in the study protocol including non-permanent fillers (e.g., HA, Calcium Hydroxyapatite) or autologous fat on or near the treated areas.
21. Subject having received within the past 9 months or planning to receive during the study any injections outside of those in the study protocol including mesotherapy or botulinum neurotoxin on or near the treated areas.
22. Subject having received at any time or planning to receive a permanent filler on treated areas (e.g., polylactic acid, Polymethylmethacrylate, silicone) during the study.
23. Subject with subcutaneous retaining structure on treated areas (meshing, threads, gold strand).
24. Subject using medication such as aspirin, nonsteroidal anti-inflammatory drugs (NSAIDs), antiplatelet agents, thrombolytics or anticoagulants within one week prior to injection visit or being a chronic user.
25. Subject undergoing a topical treatment on the test area or a systemic treatment:
 - anti-inflammatory medication and/or antihistamines within the past 2 weeks and during the study,
 - corticosteroids within the past 2 weeks and during the study,
 - retinoids and/or immunosuppressors within the past 3 months and during the study.

In terms of lifestyle

26. Intensive exposure to sunlight or UV-rays within the previous month and/or planning to do so during the study.
27. Subject planning to change her/his life habits during the study.
28. Subject with an excessive consumption of alcohol (more than 2 glasses of wine per day) and/or tobacco (more than 10 cigarettes per day).

Investigational device:

Name / code

Galenic form

VISCOL range: Injectable sterile gels in syringe

Indication	
1. VISCOL Face: Indication: malar, sub-malar, mandibular and chin areas
 
2. VISCOL Body: Indication: decolletage, neck, abdomen and internal face of the arms areas

Endpoints:	
Primary endpoint: Proportion of subjects having an improvement of the zone treated with the overall VISCOL range of devices as assessed by an independent investigator, one month (M1) after treatment, using the GAIS. An improvement is defined as a subject with "very much improved", "much improved" or "improved" score on the GAIS.
 
Secondary endpoints:
 
- Proportion of subjects having an improvement of the zone treated with the overall VISCOL range of devices as assessed by an independent investigator four months (M4) after treatment, using the GAIS.- Proportion of subjects having an improvement of the zone treated with each VISCOL device for the 2 groups independently as assessed by the independent investigator one month (M1) and four months (M4) after treatment, using the GAIS.- Proportion of subjects having an improvement of the zone treated with the VISCOL range of devices overall as assessed by the subjects, one month (M1) and four months (M4) after treatment, using the GAIS.- Proportion of subjects having an improvement of the zone treated with each VISCOL device for the 2 groups independently as assessed by the subjects, one month (M1) and four months (M4) after treatment, using the GAIS.- Change from baseline of facial skin hydration measured with Moisturmeter® one month (M1) and four months (M4) after treatment.- Change from baseline of facial skin biomechanical parameters measured with Cutometer® one month (M1) and four months (M4) after treatment.- Patient's satisfaction on the treatment outcomes using a subjective evaluation questionnaire completed at one month (M1) and four months (M4) after treatment.- Injector's satisfaction on the injection quality using a subjective evaluation questionnaire completed immediately after injection on D0.- The safety of the VISCOL range and of each VISCOL device independently will be assessed by:
• collection of immediate and early Injection Site Reactions (ISRs) by the subjects on a daily-log every day up to one month after treatment.• collection of immediate Injection Site Reactions (ISRs) by the injector immediately after treatment.• collection of ISRs by the independent investigator one month (M1) and four months (M4) after treatment.• collection of AEs throughout the study. 
Illustration of the treatment effect one month (M1) and four months (M4) after treatment compared to baseline by photographs taking.


Study Procedures:	Screening, D0, D7 (phone call for safety), M1, M4, M6 (phone call for safety)
Statistical methods:	
The statistical analysis will be performed by the CRO biostatistician.
 
The analysis of the primary performance parameter will be performed on the ITT and PP population as sensitivity analysis. The conclusion of the primary performance parameter will be performed on the ITT population.
 
The analysis of the secondary effectiveness parameters will be performed on the ITT and PP population. In case the ITT and PP population differ by less than 10%, only the PP population will be analyzed.
 
The analysis of the safety/tolerance parameters will be performed on the "safety" population.
 
A descriptive analysis of the population will be performed, including subject's characteristics, subject's disposition, deviations to the protocol, injections characteristics.
 
For the primary evaluation criteria:
 
Descriptive statistics:
 
For the parameter GAIS investigator with the 5 level scores (at M1 and M4), the frequencies and percentages will be presented for the overall face and body score and for the scores by product (separated by the 4 zones: "face", "decolletage and neck", "area abdomen" and "arm").
 
A two derived parameter will be defined based on the parameters GAIS subject and investigator as a score of 2 levels (1=Improvement (Very much improved, Much improved and Improved) and 2=No change or worsening). At each time point, these parameters will be described in frequencies, percentages and IC95% for the overall face and body score and for the scores by product (separated by the 4 zones: "face", "decolletage and neck", "area abdomen" and "arm").
 
• For group 1 : if GAIS value on face is "Very much improved", "Much improved" or "Improved" then the subject is responder (Responder='Yes') Else the subject is not responder (Responder='No')• For group 2 : if GAIS value on "decolletage and neck" is "Very much improved", "Much improved" or "Improved" then the subject is responder (Responder='Yes') Else the subject is not responder (Responder='No') 
Inferential analysis for the primary evaluation criterion
 
For the derived outcome responder rate at M1 (1 month after injection) for the GAIS Investigator, a binomial exact test (bilateral approach) vs 60% will be applied for the overall score. This test will compare the proportion of improvement to 60%.


	
In addition, a sensitivity analysis will be performed on a global binary variable based on both GAIS scores, assessed by the investigator and by the subject. If the subject is considered as improved by both scores, then the outcome will be "Improved" else the outcome will be "Not improved". This composite parameter will be summarized in frequency and percentage and presented associated with its 95% CI, by time-point for the overall face and body scores and by product (separated by the 4 zones: "face", "decolletage and neck", "area abdomen" and "arm").
 
For the secondary evaluation criteria:
 
GAIS subject : For the parameter GAIS subject with the 5 level scores (at M1 and M4), the frequencies and percentages will be presented for the overall face and body scores and for the scores by product (separated by the 4 zones: "face", "decolletage and neck", "area abdomen" and "arm").
 
Biometrological parameters: All the parameters measured with Cutometer® and Moisturemeter® will be summarized using the descriptive statistics for quantitative data for each time point (D0, M1, M4). For each parameter, a two-tailed paired t-test will be carried out to assess whether each time point after injection (M1, M4) differ significantly from the baseline value (D0).
 
Subjective questionnaire statistical analysis: The distribution of each item of the injector and subject questionnaires will be described in frequencies and percentages. For each item of the subject questionnaire, the percentage of subject satisfied, (percentages of answers "totally agree", "agree") will be computed and described in frequencies and percentages. For each item of the injector questionnaire, the percentage of answers "satisfied" or "very satisfied" will be computed and described in frequencies and percentages.
 
Safety analysis: - The injection site reactions parameters assessed by the investigator and the subject will be described. - The individual listing of AE will be provided. AE/ADE will be summarized by product. AE/ADE will be further tabulated by seriousness, severity and relationship to the investigational device and procedure.

Estimated dates of the study:	Clinical investigation beginning: Q4 2023 Clinical investigation end: Q3 2024 Expected recruitment period duration: 4 months. Clinical investigation overall duration: 6 months + recruitment period Duration by subject: 6 months + screening period

FLOW-CHART

Procedure	Visit 1 Screening	Visit 2 Day 0	Phone call 1 Day 7	Visit 3 M1	Visit 4 M4	Phone call 2 M6
Days	D-x	D0	D7 ± 1	D30±4	D120±7	D180±7
Informed consent	●					
Medical examination to check inclusion and exclusion criteria	●					
Medical history and previous/ongoing treatment(s)	●					
Confirmation of eligibility	●	●				
Urinary pregnancy test for women of childbearing potential		● ^b				
Injection by injector		●				
ISR by the injector		● ^a				
Subjective evaluation questionnaire by the injector		● ^a				
Subjective evaluation questionnaire by the patient				●	●	
GAIS by an independent investigator				●	●	
GAIS by the subjects				●	●	
ISR by an independent investigator				●	●	
ISR by the subjects		● Each day during 1 month after injection, on the daily-log				
Group 1: Macrophotographs (full face + 2 profiles)		● ^b		●	●	
Group 1: Cutometer® + Moisturemeter®		● ^b		●	●	
Group 2: Macrophotographs of the treated zone(s)		● ^b		●	●	
Adherence control, record of AE, concomitant treatments	●	●	●	●	●	●
End of study form						●

a : after injection, b : before injection

AE: Adverse Event – GAIS: Global Aesthetic Improvement Scale- ISR: Injection Site Reaction

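### Does the unmasked M1 GAIS rating need an order-concealed reading of the D0 and M1 photographs beside it?

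*Combined protocol and SAP*

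**What the plan says.** All references are to the combined protocol and SAP, section 1.5 (overall synopsis) and its flow-chart.

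- **Design.** The Development phase row reads "Exploratory study". The Design row declares the study open and intra-individual. Every subject is injected once, on D0, and there is no comparator group.
- **Rater.** The Objectives row describes the GAIS as a clinical evaluation by an independent investigator. The flow-chart has separate lines for "Injection by injector" and "GAIS by an independent investigator", the latter marked at M1 and M4 only. The same role also handles "ISR by an independent investigator", and the Endpoints row confirms "collection of ISRs by the independent investigator one month (M1) and four months (M4) after treatment". No masking is claimed, and the baseline reference for this change rating is not stated.
- **Test.** Under Statistical methods, the three favourable GAIS categories count as response, and the M1 rate is compared with 60% by a two-sided exact binomial test.
- **Photographs.** Both groups are photographed at D0 before injection, at M1 and at M4. The Objectives row gives the purpose: "Another objective will be to illustrate the device effectiveness by realization of face and body macrophotographs". The Endpoints row says the same: "Illustration of the treatment effect one month (M1) and four months (M4) after treatment compared to baseline by photographs taking".
- **Other evidence.** Statistical methods also plans the full five-level distribution of the investigator GAIS, and a composite that counts a subject as improved only when investigator and subject both say so. Cutometer and Moisturemeter comparisons with baseline are planned in Group 1.

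**The concern.** A subjective change score from a rater who knows that everyone was treated is open to expectation. Separation from the injector removes one interest in the result, but it is not masking. In a two-arm trial such a bias might partly cancel; here one observed proportion is set against a fixed number, so it does not. The response cut-off lies at *improved*, the mildest favourable category, where a small upgrade turns a non-responder into a responder.

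Before-and-after photographs will already exist. They could be shown in concealed order and scored, which would mask time point even though treatment cannot be masked. Using them only as illustration looks like a missed and inexpensive safeguard. At stake is whether a significant result above 60% reflects the device or the rater.

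**Working it through.** **Inputs.** From the synopsis: n = 86 (64 face + 22 body), null rate 60%, two-sided exact test. Assumed: alpha 0.05, complete data, and every misrating and photograph-sensitivity figure below. The documents give none of these.

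**The plan's own figure.** The available text states no alpha, power or expected rate, so 86 cannot be reproduced from stated inputs. An expected rate of 75% with 80% power at two-sided 0.05 does give 86, but that pair is an assumption.

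**Step 1: threshold.** 60/86 gives p = 0.078 and 61/86 gives p = 0.047, so at least 61 responders (70.9%) are needed. P(X ≥ 61) at a true 60% is 2.3%.

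**Step 2: effect of over-rating.** If a share u of unimproved subjects is rated improved, the observed rate is t + (1 − t)u, where t is the true rate.

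| t | u | Observed rate | P(X ≥ 61) |
|---|---|---|---|
| 0.60 | 0 | 0.60 | 2.3% |
| 0.60 | 0.05 | 0.62 | 5.3% |
| 0.60 | 0.10 | 0.64 | 10.9% |
| 0.60 | 0.20 | 0.68 | 32.4% |
| 0.55 | 0.10 | 0.595 | 1.9% |
| 0.55 | 0.20 | 0.64 | 10.9% |

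If 5% of improved subjects are also under-rated, the third row becomes 0.60 × 0.95 + 0.40 × 0.10 = 0.61, with probability 3.6%. The estimated rate is inflated at any true rate below 100%, by (1 − t)u. For t = 0.60 and u = 0.10 that is 0.04, or 86 × 0.04 = 3.4 subjects.

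**Step 3: could a masked reading see this?** Take 52 improved and 34 unchanged subjects, with 10% of the unchanged misread in each direction (34 × 0.10 = 3.4, rounded to 3). Then 52 + 3 = 55 are scored better at M1: 55/86 = 64.0%, exact 95% CI 52.9% to 74.0%. The half-width is (74.0 − 52.9)/2, about 11 points, against a shift of 4.

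Cross-tabulating by subject uses the pairing and is sharper, but 3 discordant subjects all in one direction give an exact sign-test p of 2 × 0.5³ = 0.25. With u = 0.20, 86 × 0.40 × 0.20 = 6.9, about 7 discordant subjects, and 2 × 0.5⁷ = 0.016. So a perfect reading could detect heavier over-rating.

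**Step 4: an imperfect reading.** If photographs show 80% of true improvements, a true 60% reads as 0.60 × 0.80 = 48%, 12 points lower with no over-rating. In subjects, 52 × 0.20 = 10.4 would be improved at the visit and unchanged in the photograph. That is the same pattern that over-rating produces, and more than the 7 from u = 0.20.

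Subtracting the D0-better count does not repair this. With 80% sensitivity and 10% misreading each way among the rest:

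- visible improvements: 52 × 0.80 = 41.6
- remainder: 86 − 41.6 = 44.4
- misread each way: 44.4 × 0.10 = 4.4
- M1 better 41.6 + 4.4 = 46.0; D0 better 4.4; difference 41.6, not 52.

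**Step 5: checks already planned.** The five-level table shows how much of the primary rate rests on *improved*, the category where upgrading would act. The composite can only lower the rate. The instruments give objective measures of skin quality in 64/86 = 74% of subjects, and the inclusion criteria recruit people who seek a skin-quality product.

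**The case for a change.** The strongest case for a change is that it costs little. The photographs exist, no visit or procedure is added, the visit GAIS stays primary, and one reading session with coded pairs would be the only masked evidence in the study. The planned checks do not replace it: the composite contains the same unmasked rating plus that of a subject who knows about the treatment, and the instruments omit Group 2 and do not measure aesthetic improvement. Calling the study exploratory does not remove the formal test, whose conclusion is assigned to the ITT population.

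Much of this stands. The rating is not stated to be masked, and none of the planned analyses would show expectation bias directly. What does not stand is that the extra reading would show it. If the same investigator reads the images, recall of subjects seen at M1 and M4 weakens any agreement; a new reader avoids recall but not insensitivity. The synopsis describes the photographs as illustrative and sets no standard for scoring them, so their suitability is unknown. Leaving out subjects with a visible reaction at M1, to protect the masking, would select on a post-treatment event.

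The unstated baseline reference is a detail that a synopsis commonly leaves to the rating instructions. A clinical evaluation does not exclude consulting the D0 photograph.

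**Conclusion.** No change follows. Unmasked rating is an openly declared feature of an exploratory single-arm study in which treatment cannot be concealed, and the rater is listed separately from the injector. Upward bias of unknown size would add directly to the responder rate. With 86 subjects, alpha 0.05 and a true rate of 60%, over-rating of 10% adds 4 points and raises the chance of a significant result above 60% from 2.3% to 10.9%; at a true 55% the chance is 1.9%.

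An order-concealed reading would leave the primary result as it is. It could not resolve a shift of that size, and it could not separate larger over-rating from photographs that miss real improvement. Whether to run one as an exploratory extra is a judgement on which statisticians could fairly differ. The interpretation can be handled in reporting: name the unmasked rating as a limitation, say what baseline the rater used, and read the primary rate beside the planned five-level table. All misrating and sensitivity rates here are assumptions, and the conclusion is confined to the synopsis and flow-chart.

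### When ITT and PP are close, the secondary effectiveness endpoints are analysed on PP alone, so the plan drops the set on which it concludes its own primary endpoint

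*Combined protocol and SAP*

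**What the plan says.** All the relevant text is in section 1.5, the overall synopsis.

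- **Primary endpoint** (Statistical methods row): "The analysis of the primary performance parameter will be performed on the ITT and PP population as sensitivity analysis". The next sentence settles which set decides: "The conclusion of the primary performance parameter will be performed on the ITT population".
- **Secondary effectiveness** (same row): ITT and PP by default, followed at once by the exception: "In case the ITT and PP population differ by less than 10%, only the PP population will be analyzed". Its position ties the exception to secondary effectiveness. Safety has its own population.
- **Outputs clearly under the rule**, because they sit under the secondary criteria: the five-level subject GAIS ("For the parameter GAIS subject with the 5 level scores (at M1 and M4), the frequencies and percentages will be presented"), the instrument measurements ("a two-tailed paired t-test will be carried out to assess whether each time point after injection (M1, M4) differ significantly"), and the questionnaires.
- **Outputs whose population is unclear**: the Endpoints row lists as secondary the overall investigator GAIS at M4 ("as assessed by an independent investigator four months (M4) after treatment, using the GAIS"), the per-device investigator GAIS at M1 and M4, and the subject-rated improvement rates. The Statistical methods row describes the corresponding analyses under the primary criteria ("For the parameter GAIS investigator with the 5 level scores (at M1 and M4), the frequencies and percentages will be presented"; "A two derived parameter will be defined based on the parameters GAIS subject and investigator as a score of 2 levels"). It does not say which population rule governs them.

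No reason is given for keeping PP rather than ITT, and nothing in the supplied text restores ITT.

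**The concern.** If two analysis sets nearly coincide, it is reasonable to report only one. The one to keep is the set on which the plan draws its conclusions. Here the rule does the reverse. PP is formed by removing subjects after the event, and those removals can be related to outcome. Two sets close in size can then give different results, and with no ITT figure beside the PP figure a reader cannot see the difference.

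The trial has no control arm, so rates and changes from baseline are read at face value and depend directly on who is in the denominator. If the rule also covers the M4 investigator GAIS, the M1 result is concluded on ITT while the same scale at M4 may be reported on PP only, and the two time points lose a common set.

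The trigger is also loosely worded. It does not say whether 10% refers to subjects or to results, what the base is, or whether it applies overall or per group. Headcount is the natural reading. If results were meant, ITT would have to be computed to apply the rule and would then go unreported.

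**Working it through.** The plan states no figure for the expected difference between ITT and PP, so there is none to reproduce. The calculations below show how far the rule can reach.

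**Inputs.** Planned sizes from the Planned Sample Size row: 86 = 64 (Face) + 22 (Body). Threshold: less than 10%. Assumptions: 10% means headcount, and ITT equals the planned number. The responder and satisfaction counts and the size of the instrument effect are illustrative; the documents give none.

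**1. How many subjects can be excluded before ITT is reported again**

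| Base | Largest number under 10% | Next number |
|---|---|---|
| ITT = 86 | 8/86 = 9.3% | 9/86 = 10.5% |
| PP | 7/79 = 8.9% | 8/78 = 10.3% |
| ITT = 80 | 7/80 = 8.75% | 8/80 = 10.0% (not under 10%) |
| Face alone, 64 | 6/64 = 9.4% | 7/64 = 10.9% |
| Body alone, 22 | 2/22 = 9.1% | 3/22 = 13.6% |

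If the rule is applied overall only, all 8 could come from Body: 8/22 = 36%, leaving 14 of 22 subjects behind that group's secondary results.

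**2. Effect on a proportion.** With x positive out of 86 and 8 excluded, of whom k are positive, PP = (x − k)/78. Intervals are exact (Clopper-Pearson) 95%.

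| | ITT | Exclusions mirror ITT | All 8 negative (k = 0) | All 8 positive (k = 8) |
|---|---|---|---|---|
| Questionnaire item | 69/86 = 80.2% (70.2–88.0) | k = 6: 63/78 = 80.8% (70.3–88.8) | 69/78 = 88.5% (79.2–94.6) | 61/78 = 78.2% (67.4–86.8) |
| Responder rate, if the rule covers it | 56/86 = 65.1% (54.1–75.1) | k = 5: 51/78 = 65.4% (53.8–75.8) | 56/78 = 71.8% (60.5–81.4) | 48/78 = 61.5% (49.8–72.3) |

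The last two columns are bounds, not expected effects.

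**3. Effect on the paired t-tests** (Face, 64 measured, 6 excluded, PP n = 58). Let the 6 improve by d SD less than the rest, with SD 1 within each set.

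- Shift in mean = (6/64) × d: 0.047 SD at d = 0.5 and 0.094 SD at d = 1.0.
- A PP result at exactly p = 0.05 has mean 2.002/√58 = 0.263 SD.
- ITT mean = 0.263 − 0.09375d. ITT SD = √[(57 + 5 + 58 × (6/64) × d²)/63]. t = mean/(SD/8), with 63 degrees of freedom.

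| d | ITT mean | ITT SD | t | ITT p |
|---|---|---|---|---|
| 0 | 0.263 | 0.992 | 2.12 | 0.038 (0.039 if SD is held at 1) |
| 0.5 | 0.216 | 1.003 | 1.72 | 0.090 |
| 1.0 | 0.169 | 1.035 | 1.31 | 0.196 |
| −0.5 | 0.310 | 1.003 | 2.47 | 0.016 |

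Starting at p = 0.05 is a boundary case. From a PP mean of 0.40 SD (p = 0.0035), the same formula gives ITT p = 0.0065 at d = 0.5 and 0.021 at d = 1.0, so significance at 5% would hold.

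Subjects with no follow-up value leave the paired test in either set, so this calculation concerns excluded subjects who were measured.

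**The case against.** The strongest reply is about weight. The primary conclusion stays on ITT, safety is untouched, and the study is labelled exploratory. Most affected outputs are frequencies and percentages with no threshold test. With one arm there is no randomised comparison for exclusions to break, which is the usual main reason for preferring ITT. The rule also limits itself: it applies only to small differences, and exclusions that mirror ITT move the illustrative rates by 0.3 and 0.6 points. If exclusions were unrelated to outcome, the chance that all 8 came from the 30 non-responders among 86 would be about 0.01%. Disposition and protocol deviations are to be reported, so readers would see how many subjects deviated. The supplied text is a synopsis without ITT or PP definitions, so the base of the 10% and its use per group may be set out elsewhere.

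Most of this stands, and it limits the severity. The large shifts need one-sided exclusions, the p = 0.05 case is a knife edge, and the missing definitions should not count against the plan.

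It does not rescue the rule. A single-arm estimate can still be biased by selective exclusion. A count of deviations does not show the excluded subjects' results. None of these points is a reason to keep PP rather than ITT when only one is to be reported.

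**Conclusion.** The concern holds. The plan states a rule that, for secondary effectiveness, keeps the exclusion-prone set and drops the set it relies on for its primary conclusion. On the headcount reading with 86 in ITT, it can hide the ITT result for up to 8 excluded subjects (7 if the base is PP).

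In the illustrations, the effect on a proportion runs from under 1 point when exclusions mirror ITT to about 8 points upward or 4 points downward at the extremes. For the instrument means it is 0.05 to 0.09 SD, enough to change a borderline t-test but not a clear one. These sizes rest on assumed counts and on exclusions related to outcome, which the documents neither show nor rule out; the bias can run either way.

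This should be fixed but is not critical: the primary conclusion and safety do not depend on it.

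**What to change.** Replace the exception with:

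> All secondary effectiveness endpoints, including investigator GAIS at M4 and per-device GAIS, are analysed and concluded on the ITT population. The PP analysis is supportive and may be omitted if fewer than 10% of ITT subjects, overall and in each group, are excluded from PP.

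This keeps the economy the rule was after and defines the 10% by headcount with ITT as the base. It stops exclusions from concentrating unseen in Body, and it assigns a population to the GAIS outputs that now fall between the primary and secondary headings.

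The cost is two sentences and no extra data, since ITT is already needed for the primary analysis. Reported secondary results may shift slightly, in either direction. How a missing GAIS is counted is a separate matter that this change does not settle.
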